 - b. Effects on youth violent antisocial behavior, SUDs, and risky sexual behavior will be more pronounced among males with the MAOA-LPR low activity alleles compared to males with MAOA-LPR high activity alleles, and among both males and females with 2 copies of the high-activity Val allele of the COMT Val158Met polymorphism compared to those with 2 copies of the low-activity met allele or heterozygotes.
 - c. Effects on maternal SUDs will be concentrated among mothers with 2 copies of the Val158 alleles.
 - d. Effects on child outcomes will be more pronounced among youth born to mothers with either 1) the S/S, S/L_G and "L_G/L_G" (low-activity) genotypes of 5-HTTLPR (conferring susceptibility for depression under adversity) or 2) 2 copies of the high activity COMT Val158 allele (conferring susceptibility to compromised ECF and SUDs under conditions of adversity).
8. **(Secondary)** Program effects on adolescent functioning will be explained by its improvement in prenatal health, early care of the child, maternal life-course, and earlier child academic and behavioral functioning.

Examination of Intervention Effects on Subsequent Children

With an administrative supplement, we addressed the following questions focused on subsequent children born within 5 years of the first child. Note that these questions were framed with no specific hypotheses about the degree to which particular subgroups would benefit from the intervention, given that intervention impact on pregnancy planning had been most pronounced on women with higher psychological resources.

1. To what degree does this program improve the health and development of subsequent children in terms of their a) language, academic, and executive cognitive functioning (ECF); b) depression and anxiety; c) failed conduct grades, d) violent behavior and gang membership, and e) arrests, juvenile detentions, and convictions, especially for violent crimes?
2. To what degree does this program reduce subsequent children's risk for HIV infection, including a) use and abuse of substances; b) risky sexual behaviors; c) sexually transmitted infections (STIs) and d) pregnancies?

3. To what degree are the program effects on subsequent children more pronounced for a) males, b) those born to high-resource mothers, and c) those living in the most disadvantaged neighborhoods at registration?

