We examined mediation in models with simultaneous equations, testing the significance of direct and indirect effects and their equality using methods outlined by Mackinnon.²³³ We investigated models where the intervention had a significant effect through child age 2 on outcomes significantly different at this phase in the low psychological resource group.

While missing data in this trial were remarkably low, especially at this 18-year follow-up, we were sensitive to the potential pitfalls of only analyzing cases with complete data. We have a paper in the pipeline that indicates that at child age 12 estimates of treatment-control differences would have been reduced dramatically had we discontinued sample recruitment at levels retention often is considered acceptable for studies like this (70-80%), and that these reductions in treatment effects are not simply a reflection of statistical power or differences in measured baseline characteristics.¹⁸³ There are likely differences in life-course trajectories not explained by measured baseline characteristics. We have complete data on all relevant background characteristics. Our primary strategy has been to minimize attrition to greatest extent possible. We will consider comparing our analyses to the same analyses employing multiple imputation.²³⁴ For the multiple imputations, we generally would use a Markov Chain Monte Carlo method to impute enough data to have a monotone missing data pattern. Once we have a monotone missing data pattern, we would employ imputation approaches appropriate for the type of data (continuous, dichotomous, or low frequency count data). We will perform sensitivity analyses to ensure that results are similar under various assumptions. In general, given very low attrition, such approaches are not warranted.

Examination of Hardy-Weinberg Equilibrium. We calculated allele frequencies for each polymorphism examined in this study (5-HTTLPR, MAOA-LPR, COMT Val158Met) to determine whether

the sample is in HWE. Given the relatively small sample sizes involved in these calculations, we relied upon absolute deviations from HWE in addition to formal statistical significance in making determinations as to whether the polymorphisms are in HWE.²³⁶

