
Hypothesis 8(Secondary): Program effects on adolescent functioning will be explained by its improvement in prenatal health, early care of the child, maternal life-course, and earlier child functioning. Tests of mediation will follow the theoretical model of Figure 1 and use the methods described above. To illustrate, we have hypothesized that nurse visitation will have an indirect effect on adolescent academic performance through its effect on maternal-life course. To test one aspect of this hypothesis, we will regress academic performance on treatment condition and density of subsequent children born to the mother; we will also regress density of subsequent children on intervention condition. If the paths from intervention to density and from density to academic performance are both significant, we will have met the joint significance test criterion. We will next calculate the indirect effect, based on these same two path coefficients, and compare the resultant z’ to Mackinnon’s table of critical values. If the z’ is equal to or higher than the appropriate critical value, we will conclude that density of subsequent children mediates the effect of nurse visitation on academic outcomes.

REFERENCES

1. Olds DL. Prenatal and infancy home visiting by nurses: from randomized trials to community replication. *Prev Sci*. 2002;3(3):153-172. **PubMedID: 12387552. Not available for free.**

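### The mediation analysis is screened on significant effects by child age 2, which does not match Hypothesis 8 and biases the reported indirect effects upward on average

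*Protocol*

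**What the plan says.** Three places in the protocol bear on this.

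- *Statistical Models and Methods of Analysis* gives the rule for which mediation models were examined: "We investigated models where the intervention had a significant effect through child age 2 on outcomes significantly different at this phase". The sentence ends by placing the outcome condition in one subgroup: "significantly different at this phase in the low psychological resource group".
- *Maternal and Child Outcomes (Not Revised)*, item 8 (secondary), attributes effects on adolescent functioning to "improvement in prenatal health, early care of the child, maternal life-course, and earlier child academic and behavioral functioning". It sets no age limit, significance condition or subgroup.
- *Tests of Hypotheses*, Hypothesis 8, repeats the four domains and adds: "Tests of mediation will follow the theoretical model of Figure 1 and use the methods described above". Its worked example would conclude that "density of subsequent children mediates the effect of nurse visitation on academic outcomes" if the product of the two paths is large enough. It first applies a joint significance criterion: the path from program to mediator (path a) and the path from mediator to outcome (path b) must both be significant.

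Under *Subsequent Pregnancy*, density is defined over the 18 years after the first birth. The same section then says that the subsequent-pregnancy variables were dropped as outcomes in this phase. In the list of figures, all four mediation figures (12 to 15) use a mediator measured at child age 2.

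**The concern.** Hypothesis 8 is the protocol's test of how the program works. It points back to the general methods section, so the screen described there appears to govern it. Two things follow.

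First, the rule is narrower than the hypothesis. A mediator that arises after age 2 cannot enter, although the hypothesis names domains that extend well beyond age 2 and the worked example relies on one such variable.

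Second, path a is used to choose the model and then forms part of the reported indirect effect, in the same data. Unless power for path a is high, an estimate kept because it was significant is too large on average. Pairs that failed the screen are not shown, so the reader cannot see how many were considered. Support for the program model could look stronger than the data warrant.

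**Working it through.** **Step 1: the texts side by side.**

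| Feature | General methods section | Hypothesis 8 |
|---|---|---|
| Timing of mediator | Through child age 2 | No limit; includes earlier academic and behavioral functioning |
| Mediator effect | Must be significant | No condition for inclusion |
| 18-year outcome | Must differ significantly in the low-resource group | Adolescent functioning in general |
| Example | Figures 12 to 15, all age-2 mediators | Density of subsequent children, an 18-year variable |

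Taking the domains in turn: prenatal health and early care fall inside the age-2 window. Maternal life-course is cut off at age 2. Child functioning is also cut off: the behavior checklist was used at age 2 (*Behavior Problems and Mental Disorders*) and Table 1 has child responsiveness at 6 to 24 months, but the achievement, conduct, internalizing and substance-use measures in Table 1 at ages 6 to 12 are outside the window.

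**Step 2: inputs for the size of the bias.** The protocol gives no sample size, power or bias figure for mediation, so there is none to reproduce.

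- Youth assessed at 18: 435 control, 194 nurse-visited (Table 2).
- Path a in SD units, absolute values from Table 1: HOME score 0.21 low-resource, 0.24 whole sample; beliefs associated with child abuse 0.29 low-resource, 0.23 whole sample.
- Assumed: low-resource group is half the assessed youth (218 and 97), with 40% (174 and 78) and 60% (261 and 116) also run; path b = 0.2; two-sided 5% tests; 18-year numbers used for path a.

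**Step 3: screening on path a alone.** With SE = √(1/n₀ + 1/n₁) and λ = a/SE:

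- P(significant) ≈ Φ(λ − 1.96)
- mean estimate given significance ≈ a + SE·φ(1.96 − λ)/Φ(λ − 1.96)

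For 218 and 97, SE = √(1/218 + 1/97) = 0.122.

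- a = 0.21: λ = 1.72; power 0.41; mean 0.21 + 0.122 × 0.388/0.405 = 0.327, ratio 1.56.
- a = 0.29: λ = 2.38; power 0.66; mean 0.29 + 0.122 × 0.366/0.661 = 0.358, ratio 1.23.

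For all 629 youth, SE = √(1/435 + 1/194) = 0.0863.

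- a = 0.23: λ = 2.66; mean 0.23 + 0.0863 × 0.311/0.759 = 0.265, ratio 1.15.

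Path b is not selected on here, so these ratios carry over to the indirect effect a × b.

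**Step 4: adding the outcome screen.** Simulation, 40,000 runs per setting, with c the total effect:

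| n control / nurse | a | c | True a×b | Mean, all runs | Mean, a and c significant | Ratio |
|---|---|---|---|---|---|---|
| 218 / 97 | 0.21 | 0.20 | 0.042 | 0.042 | 0.066 | 1.58 |
| 218 / 97 | 0.29 | 0.29 | 0.058 | 0.058 | 0.073 | 1.25 |
| 174 / 78 | 0.21 | 0.20 | 0.042 | 0.042 | 0.073 | 1.73 |
| 174 / 78 | 0.29 | 0.29 | 0.058 | 0.058 | 0.078 | 1.34 |
| 261 / 116 | 0.21 | 0.20 | 0.042 | 0.042 | 0.061 | 1.46 |
| 261 / 116 | 0.29 | 0.29 | 0.058 | 0.058 | 0.069 | 1.18 |
| 435 / 194 | 0.23 | 0.12 | 0.046 | 0.046 | 0.055 | 1.20 |
| 435 / 194 | 0.24 | 0.20 | 0.048 | 0.048 | 0.055 | 1.15 |

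The last two rows apply both screens in the whole sample. For 218 and 97, the ratio is 1.03 to 1.06 at a = 0.50 and about 3 at a = 0.10. Without the screen the mean equals the truth. Most of the bias comes from path a: in the first row, screening on a alone gives 0.065 and on c alone 0.047.

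**Step 5: what the screen does not do.** With b = 0, the mean indirect effect stays near zero and path b is significant in about 5% of selected runs. With a = 0 and b = 0.2, about 5% of all runs meet joint significance, but about 95% of those that pass the screen do. The error rate over all candidates is unchanged; a reader shown only the survivors cannot recover it. The proportion mediated is not consistently inflated: at a = 0.21 and c = 0.20 it is 0.21 both in truth and after selection, and it falls when c is small.

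**The case against.** The strongest reply has several parts.

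- *The rule may not be exclusive.* The sentence in the general methods section is in the past tense and does not say that no other models were run, and density is offered only as an illustration. This softens the conflict. But the Hypothesis 8 text refers back to those methods, and the listed figures fit the narrow reading, so the passages still need reconciling.
- *The domains are not shut out.* A reader might infer that the Hypothesis 8 mediators cannot be tested at all, or that two of the four domains are lost. The documents do not support that. Two domains fit the window, and the other two are cut off at age 2 rather than removed.
- *The subgroup is unclear.* The low-resource condition plainly attaches to the 18-year outcomes. Whether the mediator effect also had to be significant there is not stated. In Table 1 both caregiving measures have p = .003 in the whole sample, and screening there gives the smaller ratios. This stands, and is why both ranges are given.
- *A significant path a is already required.* The joint significance test asks for it, so a reader who infers more false claims of mediation would be wrong. This stands too; the bias is in the size of the estimate.
- *An outcome effect is presupposed.* Hypothesis 8 speaks of explaining program effects, so requiring a total effect is a defensible choice of method. It adds little bias, though it does drop pairs with an indirect effect and no significant total effect.
- *A list of pairs can sit in an analysis plan that is not shown.* True, but the point here is a rule the protocol states and its conflict with the hypothesis.

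**Conclusion.** The point holds in limited form. The selection rule and Hypothesis 8 do not agree, and following the rule leaves mediators after age 2 unexamined, including the protocol's own example. Selecting on path a biases the reported indirect effect upward on average: 1.18 to 1.73 times if the screen was applied in the low-resource group, 1.15 to 1.20 times if in the whole sample, and little when path a is large. These figures rest on an assumed low-resource share of 40 to 60%, path b of 0.2, and path a at the Table 1 values. Overestimation is an average tendency; a reader might take it as certain for every model, which the calculation does not show. Hypothesis 8 is secondary and the primary treatment contrasts are unaffected. What changes is how far the mediation results can be read as support for the program model.

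**What to change.** - Reconcile *Statistical Models and Methods of Analysis* with the Hypothesis 8 text, and say whether density of subsequent children, dropped as an outcome, is still a mediator and over what period.
- Remove the age-2 limit and the significance condition on path a.
- Fit mediators from all four Hypothesis 8 domains, measured before the 18-year visit, for a fixed list of outcomes and a stated analysis group.
- Report every indirect effect with its interval whatever its significance. Use an effect measure suited to binary, count and survival outcomes, for which a simple product of coefficients is not directly suitable.
- Label any model chosen because its effects were significant as exploratory, and state how many candidate pairs were screened.

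The data already exist. The cost is more models, some extra work on the non-continuous outcomes, a longer table with null results, and many secondary comparisons that must be read as such.

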3. **(Primary)** The program will improve the health and development of firstborn children who will exhibit: a) superior cognitive, language, and academic functioning, and executive cognitive functioning (ECF); b) less depression and anxiety; c) fewer failed conduct grades and school disciplinary actions, d) less violent behavior and gang membership, and fewer arrests, juvenile detentions, and convictions – especially for crimes involving interpersonal violence.

4. **(Primary)** The program will reduce youth risk for HIV infection, including a) use of substances and SUDs; b) risky sexual behaviors; c) sexually transmitted infections (STIs) and d) pregnancies.
5. **(Primary)** Program effects on youth will be more pronounced for a) males, b) those born to low-resource mothers, and c) those living in the most disadvantaged neighborhoods at registration.

Revised Child Outcome Hypotheses

3. **(Primary)** The program will improve the health and development of firstborn children who will exhibit: a) superior cognitive, language, and academic functioning; b) less depression and anxiety; d) less gang membership, and fewer arrests, convictions, and self-reported antisocial behavior - especially for crimes involving interpersonal violence.
4. **(Primary)** The program will reduce youth risk for HIV infection, pregnancies, births, use of substances, and SUDs.
5. **(Secondary)** The program will improve firstborn children's executive cognitive functioning (ECF); and rates of high school graduation.
6. **(Primary)** Program effects on cognitive, language, and academic functioning, and executive cognitive functioning will be more pronounced among those born to low-resource mothers and on arrests and convictions among females.

Maternal and Child Outcomes (Not Revised)

7. **(Secondary)** Program effects on mothers and youth, in preliminary analyses, will be more pronounced for those with genetic vulnerabilities:
 - a. Effects on youth depression and anxiety will be greater for those with low-activity genotypes (S/S, L_G/L_G, S/L_G) of the serotonin transporter gene (*SLC6A4*) promoter polymorphism, 5-HTTLPR, compared to those with high-activity genotypes (L_A/L_A); effects on these outcomes will be of intermediate magnitude for those with intermediate activity-level genotypes (S/L_A, L_A/L_G).

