Original Sample Characteristics. We invited 1,290 women from the obstetrical clinic of the Regional Medical Center in Memphis to participate. We recruited women <29 weeks pregnant if they had no previous live births, no specific chronic illnesses thought to contribute to fetal growth retardation or preterm delivery, and at least 2 sociodemographic risks: a) unmarried, b) less than 12 years of education, c) unemployed. Eighty-eight percent (1138/1290) completed informed consent and were randomized to 1 of 4 treatment conditions described below. All low-income women in Memphis registered for prenatal care at this clinic, which meant that we enrolled nearly the entire population during the 1990–1991 enrollment period. The study was designed to follow 742 families in two treatment conditions after delivery. 92% of the women were African-American, 98% were unmarried, 67% were <19 years of age at registration, 85% came from households with incomes < federal poverty guidelines, and 9% smoked cigarettes. At randomization, there were no treatment differences in women's background characteristics.

Randomization. After the completion of informed consent and baseline interviews, identifying information on participants was entered into a computer program that randomized women to treatment conditions. The randomization methods were extensions of Soares and Wu.¹⁸² The model on which we based the randomization included 5 classification factors: maternal race, chronological age (4 levels), gestational age at enrollment, employment status of head of household and geographic region of residence (4 regions).

Statistical Power in the Original Design. We conducted power calculations to determine the number and proportion of subjects to assign to treatment and control conditions while minimizing costs in the initial study period (prenatal through child age 2). This allowed disproportionate assignment of women to treatment and control conditions and a reduction in number of families followed into the postnatal phase of the trial. Given high rates of sample retention, the original power calculations hold.

Treatment Conditions

Treatment 1 - Transportation during Pregnancy. The 166 families in this treatment condition received free round-trip taxicab transportation for scheduled prenatal care appointments. This group did not receive any postpartum services or assessments.

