As shown in Table 4, we evaluated the first-born children using *tests* of intellectual functioning, language, neurocognitive skills, and academic achievement; *interviews*; and *abstractions* of electronic school records and state foster care data. Moreover, we conducted direct assessments of adolescents' physical health, focusing on the presence of STDs use of substances through urinalysis, blood pressure, and weights and heights. We gathered DNA for genotyping, using Oragene (described below). Gathering these data will be integrated into an overall physical health assessment that includes measures of obesity, and hypertension. Youth were provided counseling for STI's and substance use; those with identified STI's were asked to return to the study physician to obtain confidential, one-dose treatment for detected pathogens.

Table 4. Constructs, Variables, and Source of Data for Assessments of Youth

Outcome Domain	In-Person Interview	Direct Assess	Admin Records	Parent Report
Cognitive and Language Abilities		X		
Executive Functions (risky decision making, impulsivity, facial recognition, verbal working memory)		X		
Behavior Problems/Mental Disorders (Depression/Anxiety)	X			
Substance Use and Disorders	X	X		
Sexual Behavior/Pregnancies	X	X		
Sexually Transmitted Infections		X		
High School Graduation	X		X	
Violent Criminality and Gang Membership	X			
Arrests, Convictions, and Juvenile Detention	X			X
Foster Care Placements			X	X
Violence Exposure (home, school, and community) – DID WE RETAIN THIS?	X			
Vulnerability Genes (MAOA, 5-HTT, COMT)		X		

Cognitive and Language Abilities. We conducted tests of intellectual and language ability to trace trajectories in these functions over time and to sort out program impact on ECF from general intelligence and language. We chose 2 tests that could be conducted by non-clinicians: the 4th edition of the Peabody Picture Vocabulary Test–III (PPVT), which we administered to firstborn children at age 6; and the Matrices subtest from the Kaufman Brief Intelligence Test (KBIT–2). The Matrices is a non-verbal, visual problem-solving test with both concrete and abstract tasks. The KBIT is a brief version of the IQ measure also used with firstborn children at age 6.¹⁹⁵

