The primary analyses made use of general linear model methods and their extensions. The focus was on full model specification to account for all sources of variation, and a full examination of interactions among model factors. The primary classification factors for examination in our models, as determined by our hypotheses and earlier work, include treatments (Control vs. Nurse Visited - T), maternal psychological resources (low versus high – P), and sex of child (S). Standard covariates included an index of household poverty, maternal beliefs associated with child abuse, and for child outcomes, age of the child at the 18-year interview. Genetic analyses included the gene as an additional classification factor and were interacted with treatment status only (see more information below). We employed pared-down versions of full model specification when we had infrequently occurring outcomes (e.g. convictions for interpersonal violence). In general the approach involved beginning with a fully specified model and continuing to eliminate non-significant interactions unless a specific a priori hypothesis forced the interaction term(s) into the model.

Continuous variables were run with a general linear model; dichotomous variables with binomial error distributions; low frequency count variables with negative binomial distributions. For outcomes measured over the life course, the above models were extended to mixed or generalized mixed models to account for correlated data (random effects for time with unstructured variance terms). Subsequent children analyses were also run with mixed or generalized mixed models to account for correlation within the same family. We were interested in the treatment effects for subsequent children alone, as opposed to an overall family effect that would include the first born children.

We employed Cox proportional hazard models²³² for outcomes with a survival component. We present in the tables adjusted hazard rates at age 18 since the vast majority of the sample was interviewed after their 18th birthday but rapidly drops off after this date. The methods used for the mortality analyses can be found elsewhere.¹¹

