Hypothesis 3a–d (primary): The program will improve the health and development of firstborn children who will exhibit: a) superior cognitive, language, and academic functioning; b) less depression and anxiety; c) less gang membership, and fewer arrests, convictions, and self-reported antisocial behavior - especially for crimes involving interpersonal violence.. We will examine this hypothesis in the model used to test hypotheses 1 and 2, after adding child sex (S) as a classification factor. We will test hypotheses 3a–d by examining each of child outcome in the saturated TxPxS (2x2x2) model, including covariates. In our first-level analysis, we will examine treatment–control differences averaging across levels of maternal psychological resources and child sex. Outcomes that have essentially normal distributions (e.g., cognitive and academic outcomes) will be examined in the general linear model. Those that have low-frequency count distributions (e.g., counts of failed conduct grades) will be examined in the generalized model. For very sparsely distributed outcomes, we may need to drop certain model terms, such as 3-way interactions or nonsignificant covariates to increase model stability. We will retain model terms with highest levels of significance and those central to the hypothesis. Finally, we will examine outcomes that have binomial distributions in the fully specified logistic model. Some outcomes, such as standardized math scores, will have multiple measures for each child at different ages, and the model will include additional repeated measures factors for child age.

Hypothesis 4 a–c (primary): The program will reduce youth risk for a) HIV infection, b) pregnancies, births, c) use of substances, and SUDs. We will employ nearly identical analytic methods for testing hypothesis 4 as we employ for testing hypothesis 3. The primary outcome(s) for HIV risk will consist of indices that we will create to quantify HIV risk exposure.

Hypothesis 5 (secondary): The program will improve firstborn children’s executive cognitive functioning (ECF); and rates of high school graduation. We will employ nearly identical analytic methods

for testing hypothesis 5 as we employ for testing hypothesis 3.. In analysis of executive cognitive functions, we will control statistically for KBIT matrices scores and PPVT to discern the impact of the program on executive functions independent of general intelligence and language.

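### The Hypothesis 5 test of executive functioning adjusts for two post-randomisation scores the program is meant to raise, so it does not estimate the effect Hypothesis 5 states

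*Protocol*

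**What the plan says.** In the protocol's Revised Child Outcome Hypotheses, no. 5 (secondary) predicts improvement in "executive cognitive functioning (ECF); and rates of high school graduation". Neither that list nor the restatement under Tests of Hypotheses limits the ECF claim to a part that is independent of other abilities.

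The Hypothesis 5 analysis paragraph takes over the Hypothesis 3 methods, that is, the treatment × maternal resources × child sex model with covariates. It then adds one ECF-specific sentence: "we will control statistically for KBIT matrices scores and PPVT to discern the impact of the program on executive functions independent of general intelligence"; it names language as well. No ECF analysis without these two scores is described for Hypothesis 5.

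Other relevant statements in the protocol:

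- Hypothesis 3 (primary) expects "a) superior cognitive, language, and academic functioning; b) less depression and anxiety".
- Cognitive and Language Abilities, on the PPVT and KBIT Matrices: "We conducted tests of intellectual and language ability to trace trajectories in these functions over time and to sort out program impact on ECF". The separation meant is from intelligence and language.
- Original Sample Characteristics: "We recruited women <29 weeks pregnant if they had no previous live births". Randomization: "After the completion of informed consent and baseline interviews, identifying information on participants was entered into a computer program that randomized women".
- Statistical Models and Methods of Analysis: "Standard covariates included an index of household poverty, maternal beliefs associated with child abuse, and for child outcomes, age of the child". Age is taken at the 18-year interview. KBIT and PPVT are not among these covariates.
- The same section, on mediation: "We examined mediation in models with simultaneous equations, testing the significance of direct and indirect effects".

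**The concern.** A covariate measured after randomisation and affected by treatment is not a baseline adjuster. Holding it fixed removes whatever part of the treatment effect runs through it or travels with it. Here the two covariates stand for intelligence and language, two of the domains in which the trial expects a benefit under a primary hypothesis. The better Hypothesis 3a does, the more of the ECF effect the Hypothesis 5 model takes away.

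What is left is a direct-effect coefficient. Randomisation does not protect it, because unmeasured causes shared by the test scores and ECF can bias the conditional comparison.

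A null Hypothesis 5 result could then mean only that ECF gains came together with intelligence and language gains. It could easily be read as no ECF benefit.

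**Working it through.** **Timing and role of the covariates.** Women were enrolled before 29 weeks of pregnancy and randomised after baseline interviews, so any child test score is post-randomisation. The protocol names the PPVT and KBIT Matrices as its tests of language and intellectual ability. Table 1 already reports age-6 whole-sample program effects of 0.17 SD (PPVT, p=.04) and 0.18 SD (KABC composite, p=.03).

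**No figure to reproduce.** The protocol gives no ECF effect size, no power for ECF and no correlation of ECF with KBIT or PPVT. What follows is an illustration.

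**Inputs from the protocol.** Youth assessed at 18: 435 control, 194 nurse-visited (Table 2). Age-6 effects of 0.18 and 0.17, sum 0.35 (Table 1); the KABC effect stands in for KBIT Matrices.

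**Assumptions.** Total ECF effect 0.25 SD; correlation between the two scores 0.5; correlation r of ECF with each score 0.2 to 0.5; a share c of the age-6 effects still present at 18; two-sided 5% level.

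**Formulas.**
- Coefficient on each score: b = r/(1 + 0.5)
- Loss = c × b × 0.35
- Variance explained: R² = 2rb
- SE = √(1/435 + 1/194) = 0.0863
- Power = Φ[(0.25 − loss)/(SE × √(1 − R²)) − 1.96]
- Break-even c, below which adjustment does not lower power = 0.25 × (1 − √(1 − R²))/(0.35 × b)

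Unadjusted: 0.25/0.0863 − 1.96 = 0.94, so power is about 0.83. Example with r = 0.2 and c = 1: b = 0.133, loss = 0.133 × 0.35 = 0.047, R² = 0.053, power 0.68.

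| r | R² | c=1: loss, power | c=0.5: loss, power | c=0.25: loss, power | c=0: power | break-even c |
|---|---|---|---|---|---|---|
| 0.2 | 0.053 | 0.047, 0.68 | 0.023, 0.77 | 0.012, 0.81 | 0.85 | 14% |
| 0.3 | 0.120 | 0.070, 0.60 | 0.035, 0.76 | 0.018, 0.82 | 0.87 | 22% |
| 0.4 | 0.213 | 0.093, 0.53 | 0.047, 0.76 | 0.023, 0.84 | 0.90 | 30% |
| 0.5 | 0.333 | 0.117, 0.47 | 0.058, 0.78 | 0.029, 0.88 | 0.94 | 39% |

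As a share of 0.25 SD, the loss is 19–47% at c = 1, 9–23% at c = 0.5 and 5–12% at c = 0.25. A simulation with 4,000 runs per setting agrees: at c = 1 the mean adjusted estimate is 0.204 (r = 0.2) and 0.134 (r = 0.5), with power 0.68 and 0.47.

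**Sensitivity at c = 1.** With a correlation between the two scores of 0.3 the loss is 22–54%; with 0.7 it is 16–41%. With a total ECF effect of 0.15 SD it is 31–78%; with 0.30 SD it is 16–39%.

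**Does the adjusted coefficient at least give the direct effect?** Only without unmeasured common causes. In a simulation of 2,000,000 youths with one mediating score shifted by 0.17, the true direct effect was 0.10 and the true total was 0.10 + 0.4 × 0.17 = 0.168. With no common cause, the adjusted estimate was 0.101. With an unmeasured cause loading 0.5 on both the score and ECF, it was 0.058, while the unadjusted estimate stayed at 0.168.

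**The case against.** The adjustment is deliberate and disclosed. The protocol says twice that it wants to separate ECF from general intelligence and language, and its background section gives a neurodevelopmental reason for interest in ECF itself. Read with its method sentence, Hypothesis 5 might mean an ECF-specific effect. This stands as an account of intent. It does not change the stated hypothesis, and it does not make the direct effect identifiable by randomisation.

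The total effect may also be available already. If Hypothesis 6 fits ECF in the core model without these scores, that model yields the whole-sample difference too. But the protocol does not make that the Hypothesis 5 test. Hypothesis 6 speaks only of the core model with covariates. The plain reading is the standard covariates, yet the ECF sentence under Hypothesis 5 is not expressly limited to that hypothesis.

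The mediation section is not a ready home for this question, because it covers mediators the program had affected by child age 2. That is fair. The section shows only that the protocol treats direct effects as a separate matter.

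The sizes rest largely on assumptions. The KABC composite is not the KBIT Matrices subtest. The several ECF tasks may correlate with the scores differently, and the loss vanishes as the correlation nears zero. An effect of 0.25 SD exceeds both age-6 effects used; at 0.20 SD unadjusted power would be about 0.64. All of this is correct and limits what can be said about size, but the mismatch in the quantity estimated remains.

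**Conclusion.** The concern holds. As written, the ECF part of Hypothesis 5 is tested with a coefficient that differs from the program effect it states whenever the program shifts KBIT or PPVT and ECF is related to them. With positive relations, the estimate is too small.

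The size cannot be derived from the protocol. Under the assumptions above, the shortfall runs from nil (no persistence of the age-6 effects) to 47% of the total effect (full persistence, r = 0.5). Power is not the stable argument: when persistence is below 14–39%, depending on r, the adjusted model loses no power or gains some, yet it still understates the total effect unless persistence is zero.

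This should be fixed. It affects a secondary, whole-sample test, and no primary conclusion is shown to be at risk. On the plain reading, the Hypothesis 6 ECF contrast does not carry the adjustment.

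**What to change.** - Test the ECF part of Hypothesis 5 in the treatment × resources × sex model with the standard covariates only: household poverty, maternal beliefs associated with child abuse, and child age at interview.
- Report the KBIT- and PPVT-adjusted model beside it as a supportive direct-effect analysis, stating that it assumes no unmeasured common causes of the scores and ECF.
- Add one clause confirming that the Hypothesis 6 ECF contrast uses the standard covariates only.

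Rewording Hypothesis 5 as an effect independent of intelligence and language would also remove the mismatch, but it would rest the hypothesis on a quantity that randomisation does not identify.

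The cost is one sentence, one clause and one extra model per ECF outcome, with no new data. The main ECF result would no longer claim independence from intelligence and language, and it would give up the variance reduction from these covariates (5–33% under the assumed correlations).
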